^eFU is to be conducted on Day 31 \pm 3 days. The FU assessment may be conducted via telephone contact or by another interactive technology for subjects who were considered to be Clinical Cures ([Section 13.2.2](#)) and had no AEs or clinically significant laboratory or ECG abnormalities noted at or after the TOC visit; otherwise, the visit must be conducted in person.

^fWritten and signed informed consent must be obtained before any protocol assessment is performed.

^gComplete physical exam—consisting of general appearance, skin, eyes, ears, nose, throat, lungs, heart, abdomen, back, extremities, lymph nodes, vascular, and neurological exams—will be conducted at Screening and daily between Day 1 and Day 5 (whether inpatient or outpatient), EOT, and TOC. As part of the complete physical exam, the Investigator should assess the severity of the subject's CABP symptoms of dyspnea, cough, production of purulent sputum, and pleuritic chest pain, based upon the CABP Symptom Severity Guidance for Investigator Assessment in [Appendix III](#).

^hVital signs—including body temperature (oral, rectal, or tympanic), blood pressure, heart rate, respiratory rate, and pulse oximetry—will be collected at Screening and daily between Day 1 and Day 5 (whether inpatient or outpatient), EOT, and TOC. Height, weight, and creatinine clearance (CrCl) will also be collected at the Screening Visit.

ⁱA 12-lead ECG will be performed at Screening, Day 1, Day 3, Day 5, and EOT. A 12-lead ECG will be performed at TOC or FU if prior ECG(s) showed any clinically-significant abnormality ([Sections 11.9 and 11.10](#)).

^jSubjects must have a confirmatory CXR or chest CT scan consistent with acute bacterial pneumonia within 48 h prior to randomization.

^kSubjects with a PORT score of 51 to 105 (PORT Risk Class of II, III or IV) are eligible for enrolment ([Appendix II](#)).

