- If prior blood cultures are positive, repeated post-baseline blood cultures should be collected on the day that the positive blood culture is detected
- Repeated respiratory specimens should be obtained only if clinically indicated

PK Assessments:

- Blood samples for PK analyses will be taken from all subjects at sites where PK sampling is possible on Day 3 at the following times:
 - Within 10 minutes before study drug administration
 - 2-4 h after study drug administration
 - subjects who have been hospitalized are also required to have a post-dose PK sample at 6-10 h (Day 3)

11.5 STUDY DAY 4

Administer study drug per the schedule in [Section 10.1](#).

Clinical Assessments:

- Record one set of vital signs, including body temperature (highest daily oral, rectal, or tympanic temperature), blood pressure, heart rate, respiratory rate, and pulse oximetry
- Perform a complete physical examination
- Assess CABP symptom severity ([Appendix III](#)). CABP symptom severity information entered into the eCRF will be used to programmatically determine clinical response at Day 4 ([Section 13.2.1](#)); note this is not an Investigator-determined clinical outcome.
- Identify, assess and record any AEs
- Record any concomitant medications

Microbiological Assessments:

- If prior blood cultures are positive, repeated post-baseline blood cultures should be collected on the day that the positive blood culture is detected
- Repeated respiratory specimens should be obtained only if clinically indicated

PK Assessments:

- A single blood sample for PK analyses will be taken from all subjects at sites where PK sampling is possible on Day 4 at 24-28 h following study drug administration on Day 3

11.6 STUDY DAY 5

Administer study drug per the schedule in [Section 10.1](#).

Clinical Assessments:

- Record one set of vital signs, including body temperature (highest daily oral, rectal, or tympanic temperature), blood pressure, heart rate, respiratory rate, and pulse oximetry
- Perform a complete physical examination
- Assess CABP symptom severity ([Appendix III](#))
- Obtain a 12-lead ECG
- Identify, assess and record any AEs
- Record any concomitant medications

Central Laboratory Assessments:

- Obtain hematology, coagulation and chemistry panel ([Appendix IV](#))

Microbiological Assessments:

- If prior blood cultures are positive, repeated post-baseline blood cultures should be collected on the day that the positive blood culture is detected

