13.0 EFFICACY EVALUATION

13.1 PRIMARY AND SECONDARY EFFICACY VARIABLES

Primary efficacy variable:

- Clinical response at Day 4 (ITT population)

Secondary efficacy variables:

- Clinical response at Day 4 (micro-ITT population)
- Clinical outcome at EOT and TOC (ITT and CE populations)
- Improvement in CABP symptoms and normalization of vital signs at Day 4 (ITT population)
- Clinical outcome at TOC (micro-ITT population)
- By-subject and by-pathogen microbiological response at TOC (micro-ITT and ME populations)
- Hospitalization prior to FU (ITT population)

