13.2 CLINICAL OUTCOME ASSESSMENTS

13.2.1 Clinical Response at Day 4

The primary efficacy endpoint is clinical response (response, non-response, or indeterminate) at Day 4, tested in the ITT Population. Clinical response (response, non-response, or indeterminate) at Day 4 will also be tested in the micro-ITT Population as a secondary efficacy endpoint. Clinical response is determined programmatically using the Investigator's determination of CABP symptoms entered into the eCRF ([Table 13.2.1-1](#)). The Investigator is not responsible for categorizing subjects as clinical response, non-response, or indeterminate at Day 4. The severity of the subject CABP symptoms of dyspnea (shortness of breath), cough, production of purulent sputum, and pleuritic chest pain will be evaluated on a 4-point scale (absent, mild, moderate, or severe) based upon the CABP Symptom Severity Guidance in [Appendix III](#).

Table 13.2.1.-1. Clinical Outcome Assessment at Day 4.

Outcome	Definition
Clinical Response	Alive and programmatically-determined improvement of at least 1 level (e.g., severe to moderate, moderate to mild, mild to absent) in at least 2 CABP symptoms (dyspnea, cough, production of purulent sputum, and pleuritic chest pain) compared to Screening, without worsening in any other symptom. Severity of symptoms is based on a 4-point scale (absent, mild, moderate, or severe) (Appendix III).
Clinical Non-Response	Meets any of the following criteria: 
 • No programmatically-determined improvement of at least 1 level in at least 2 CABP symptoms compared to Screening

Table 13.2.1.-1. Clinical Outcome Assessment at Day 4.

Outcome	Definition
	
 Worsening in any of the 4 CABP symptoms compared to Screening Requires alternative rescue antibacterial therapy for CABP prior to Day 4 Death from any cause prior to Day 4
Indeterminate	Study data are missing for evaluation of efficacy at Day 4 for any reason, including lost to follow-up.

Abbreviations: CABP = community-acquired bacterial pneumonia.

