13.2.2 Clinical Outcome at EOT or TOC

An assessment of clinical outcome (cure, failure, or indeterminate) will be made by the Investigator at EOT (conducted on the day of, or within 2 days following, Day 7) or TOC (Day 15 \pm 3 days). Clinical outcome at EOT and TOC will be analyzed as secondary endpoints in the ITT and CE populations, and at TOC in the micro-ITT population.

Clinical success and clinical failure are defined in [Table 13.2.2-1](#). Clinical failure determined at any visit prior to TOC will be carried forward to subsequent assessment visits.

Table 13.2.2-1. Clinical Outcome Assessments at EOT and TOC.

Outcome	Definition
Clinical Cure	Alive and CABP is sufficiently resolved such that further antibacterial therapy is not needed. These subjects may have some residual findings related to infection (i.e., cough) requiring non-antibiotic ancillary treatment (e.g., expectorant). Criteria for clinical failure or indeterminate (below) should not be met.
Clinical Failure	Meets any of the following criteria: 
 Requires alternative rescue antibacterial treatment for CABP prior to the assessment (EOT or TOC) related to progression or worsening of CABP symptoms, development of infectious complications of CABP (e.g., empyema, lung abscess), or development of a TEAE that required discontinuation of study therapy Death from any cause prior to the assessment (EOT or TOC)
Indeterminate	Study data are missing for evaluation of efficacy at the assessment visit (EOT or TOC) for any reason, including lost to follow-up

Abbreviations: CABP = community-acquired bacterial pneumonia; EOT = End-of-Therapy; TEAE = treatment-emergent adverse event; TOC = Test-of-Cure.

13.2.3 Improvement in CABP Symptoms and Normalization of Vital signs at Study Day 4

An assessment of improvement in CABP symptoms and normalization in vital signs at Study Day 4 will be made programmatically on Day 4. Improvement in CABP symptoms and normalization in vital signs is defined in [Table 13.2.3-1](#).

Table 13.2.3-1 Improvement in CABP Symptoms and Normalization of Vital signs at Study Day 4.

Outcome	Definition

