16.2.1 Determination of Sample Size

Approximately 225 adult subjects with CABP will be enrolled in this study. Randomization will have a 1:1:1 (Arm A: Arm B: Arm C) allocation ratio; therefore, approximately 150 subjects will be randomized to receive active oral nafithromycin. The objectives of this Phase 2 study are to collect initial efficacy data and to evaluate the safety and PK of oral nafithromycin in subjects with CABP. The sample size chosen for this study is considered to be adequate to achieve the study objectives and provide sufficient data to inform the design of future definitive studies, including Phase 3 studies, of nafithromycin. Assuming a 78% clinical response rate at Day 4 in the oral nafithromycin treatment arms, the sample size of 75 subjects per treatment arm will yield a 95% confidence interval around the response rate of 66.9% to 86.7%.

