16.2.3 Efficacy Analyses

16.2.3.1 Primary Efficacy Analysis

The primary efficacy evaluation will be the by-subject clinical response at Day 4 in the ITT population. Each subject will be classified programmatically as a responder, non-responder, or indeterminate based on CABP symptom data entered in the e-CRF ([Section 13.2.1](#)).

The number and percentage of subjects in each treatment group classified programmatically as a responder, non-responder and indeterminate will be reported. Exact 95% confidence intervals around the percentage of subjects classified as responders will be calculated for each treatment group using the Clopper-Pearson Method. The treatment difference will also be determined and a 95% confidence for the difference will be calculated using the method of Miettinen-Nurminen. Individual subject data will also be displayed as a listing.

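### The protocol specifies no efficacy analysis of the graded CABP symptoms: they enter only as yes/no composites at Day 4, and none is used after Arms A and B diverge

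*Combined protocol and SAP*

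**What the plan says.** Section 13.2.1 has dyspnea, cough, purulent sputum and pleuritic chest pain "evaluated on a 4-point scale (absent, mild, moderate, or severe) based upon the CABP Symptom Severity Guidance" in Appendix III. The grading is part of the complete physical examination, which, under footnote g of Table 3-1, "will be conducted at Screening and daily between Day 1 and Day 5 (whether inpatient or outpatient), EOT, and TOC".

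The grades reach an efficacy endpoint in two places:

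- **Clinical response at Day 4** (Table 13.2.1-1; primary in ITT, secondary in micro-ITT). Response needs an improvement of one level or more in at least two symptoms and no worsening in any other. Section 11.5 confirms the source: "CABP symptom severity information entered into the eCRF will be used to programmatically determine clinical response at Day 4". The analysis is stated in Section 16.2.3.1: "Each subject will be classified programmatically as a responder, non-responder, or indeterminate based on CABP symptom data entered in the e-CRF".
- **Symptom improvement plus normalization of vital signs at Day 4** (Table 13.2.3-1; secondary in ITT). This uses the same yes/no symptom rule and adds further yes/no criteria.

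After Day 4 the clinical efficacy variable is a different one: "An assessment of clinical outcome (cure, failure, or indeterminate) will be made by the Investigator at EOT" and again at TOC (Section 13.2.2). Its definition does not refer to the grades. Section 16.2 calls the study exploratory and plans no formal comparisons. Section 16.2.1 says the sample size should "provide sufficient data to inform the design of future definitive studies, including Phase 3 studies, of nafithromycin".

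**The concern.** The responder rule discards much of what is recorded. A subject who goes from severe to absent on all four symptoms counts the same as one who improves two symptoms by one level. A subject who improves one symptom by three levels counts the same as one who does not change. In a descriptive study of 75 per arm, precision is the main thing the design can offer to Phase 3 planning, and a supportive analysis of data already collected could add to it.

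The second issue is timing. The trial compares a 3-day with a 5-day course, but the primary endpoint is read when the two arms differ by at most one active dose. The grades at Day 5, EOT and TOC are the graded efficacy data collected after that point, and the protocol names no efficacy analysis of them. It defines no efficacy endpoint of any kind at Day 5.

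**Working it through.** **1. Where the grades are collected and used** (Table 3-1, Sections 11.1 to 11.9, 13.1 to 13.3, 16.2.3)

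| Visit | Symptoms graded | Specified efficacy use of the grades |
|---|---|---|
| Screening | yes | reference level for the Day 4 rules |
| Days 1, 2, 3 | yes | none |
| Day 4 | yes | two yes/no composites |
| Day 5 | yes | none |
| EOT, TOC | yes | none; investigator's cure or failure instead |

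No section names a total score, a change from Screening or a by-visit contrast.

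**2. When Arms A and B separate.** Section 8.1 gives Arm A active drug on Days 1-3 and Arm B on Days 1-5. Treatment is the same until the Day 4 dose. The protocol does not say whether the Day 4 grading precedes or follows that dose, so 0 or 1 active dose separates the arms at the primary endpoint.

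**3. The plan's own figure.** Inputs from Section 16.2.1: n = 75, p = 0.78, so x = 0.78 × 75 = 58.5. The Clopper-Pearson limits are Beta(0.025; 58.5, 17.5) = 66.94% and Beta(0.975; 59.5, 16.5) = 86.75%. The stated 66.9% to 86.7% is reproduced. With 58/75 or 59/75 responders in both arms, the planned Miettinen-Nurminen interval for a difference is about ±13.5 or ±13.3 percentage points.

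**4. What a yes/no cut costs in principle.**

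- For a normal score cut at p, the share of information kept is φ(z)²/[p(1−p)]. At p = 0.78, z = 0.772 and φ(z) = 0.296, giving 0.296²/0.1716 = 0.51. For p from 0.70 to 0.85 the share runs from 0.58 to 0.43.
- Under proportional odds, information is proportional to 1 − Σpᵢ³. For yes/no at 78% this is 1 − (0.78³ + 0.22³) = 0.515. For 4 to 13 equally filled levels it is 0.94 to 0.99. The share kept is 0.55 to 0.52.

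Both are idealized, because the responder rule is not a simple cut of a total score. They indicate the order of the loss: roughly half.

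**5. Simulation of the Day 4 comparison.** The documents give no SD, symptom correlation or rescue rate, so all of these are assumed. The model uses four symptoms coded 0-3 (total 0-12), at least two present at Screening, a treatment effect common to all four, between-symptom correlation 0.3 to 0.9 and two baseline severity mixes. It is calibrated so that the Table 13.2.1-1 rule gives 78% v 63% at 75 v 75. The 63% is also an assumption. Two-sided 5% power serves only as a gauge of precision.

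Closed-form check of the binary figure: pooled p = 0.705; null SE = √(2 × 0.705 × 0.295/75) = 0.0745; alternative SE = √((0.78 × 0.22 + 0.63 × 0.37)/75) = 0.0735. Power = Φ[(0.15 − 1.96 × 0.0745)/0.0735] = 0.52.

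| Rescue or death (equal in both arms) | Responder | ANCOVA of total, score 12 if rescue or death | Baseline-adjusted rank analysis |
|---|---|---|---|
| none | 0.48-0.56 | 0.71-0.80 | not needed for the contrast |
| 3% to 10% | about 0.50-0.55 | 0.42-0.69 | 0.67-0.77 |

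The rank analysis stands in for a proportional-odds model. Over 0 to 10% rescue or death, the ordinal approach gives about 0.67-0.78.

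The ANCOVA result has a simple cause. If a fraction r is scored 12 and the rest have mean m and variance s², the variance becomes (1−r)s² + r(1−r)(12−m)². When most subjects have low totals, (12−m)² is large and a few such values dominate. Ranks or ordered categories do not carry that distance.

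**The case against.** **A later SAP may cover it.** Section 16.2 announces a comprehensive SAP and Section 7.3 allows exploratory analyses. That SAP is not in the available text. Section 16.2 also says that all data will be summarized, and Section 16.2.4 promises descriptive statistics for physical examinations at each time point, of which symptom grading is part. A reader might infer that no table will show the grades at all. The documents do not support that: by-visit frequencies may well appear. What stands is that no score, model or arm contrast is specified.

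**The 3-day v 5-day question is already planned for.** This is partly right. Cure at EOT and TOC is analyzed with between-group differences and 95% confidence intervals (Sections 13.1 and 16.2.3.2). A reader might infer that the duration comparison is missing. It is not; it rests on binary outcomes only.

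**The gain is model-dependent.** This stands. A shift common to all four symptoms favors a sum score. The 0-3 coding and the total are not in the protocol, which has four named levels.

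**The gain may not extend past Day 4.** This stands. By EOT and TOC, totals may cluster near zero, since the absent level includes a return to the pre-illness state for most symptoms and cure allows only residual findings.

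**It is a preference.** Nothing planned is biased or wrong, and the stated precision reproduces. The point concerns unused information in a study whose purpose is to inform later ones.

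**Conclusion.** The point holds in a limited form. The protocol uses the symptom grades for efficacy only through yes/no composites at Day 4, and specifies no efficacy analysis of them once Arms A and B differ. At Day 4, an ordinal analysis would raise power, as a gauge of precision, from about 50-55% to about 67-78%. This rests on an assumed 78% v 63% split at 75 v 75, correlations of 0.3 to 0.9, a common shift and 0 to 10% rescue or death. The gain would be smaller if one symptom carried the effect.

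Two stronger inferences are not supported. First, not every graded analysis helps: ANCOVA with a score of 12 for death or rescue can fall below the responder analysis. Second, no gain has been shown for Day 5, EOT or TOC. There the argument is only that the data exist and bear on duration.

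**What to change.** Keep the Day 4 responder endpoint as primary. In Section 16.2.3, pre-specify one supportive analysis:

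- **Variable:** symptom total, the sum of the four grades coded 0-3, in the ITT population at Day 4, Day 5, EOT and TOC.
- **Model:** proportional-odds or rank-based, adjusted for the Screening total, region and PORT class. Do not use ANCOVA with a score of 12 for death or rescue.
- **Death or rescue antibacterial therapy for CABP:** placed in the worst category.
- **Report:** A-C and B-C at each visit, and A-B from Day 5, with 95% confidence intervals.
- **Missing grades:** state the rule alongside the missing-data handling that Section 16.4 leaves to the SAP.

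Before the score is derived, reconcile Appendix III. In the cough row, the alternative descriptor (mildly above the pre-illness baseline) appears under Mild, Moderate and Severe. The existing primary endpoint uses the same row.

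The cost is SAP wording, the Appendix III reconciliation, one derived variable and one or two tables, with no new visits or subjects. The supportive result may differ from the responder result, so the text should say in advance that it is supportive. No error rate is affected, because no formal tests are planned.

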16.2.3.2 Secondary Efficacy Analyses

The secondary analysis variables are listed in [Section 13.1](#).

For analyses of the variables above that measure clinical success on a per-subject basis (i.e., clinical cure, improvement in CABP symptoms and normalization in vital signs at Day 4, lack of readmission or new admission to the hospital), the number and percentage of subjects in each treatment group in the specified population(s) classified as clinical success, clinical failure, and indeterminate (as applicable to each secondary analysis; [Section 13.2](#)) at the specified time point(s) will be tabulated. The difference between treatment groups in clinical success and 2-sided 95% CI for the difference also will be included in the tabulation.

The per-pathogen and per-subject microbiological efficacy analyses will be conducted in the micro-ITT and ME Populations at TOC. Per-subject responses will be based on per-pathogen outcomes ([Section 13.3](#)). These responses include eradication, presumed eradication, persistence, and presumed persistence. Of these responses, eradication and presumed eradication will be regarded as a favorable outcome. Persistence and presumed persistence will be regarded as an unfavorable outcome. To have an overall favorable microbiologic response, the outcome for each baseline pathogen must be favorable. Microbiological outcomes in the ME Population, by definition, will not include subjects with indeterminate responses.

The number and percentage of subjects in each treatment group recorded as having a favorable and unfavorable microbiologic response will be tabulated. Since this is an exploratory study, no statistical comparison between treatment groups is planned. In addition, a table summarizing the number and percent of all responses for each treatment group will be displayed. Individual subject data will also be displayed as a listing.

Emergent infections (i.e., superinfection, new infection) will not be considered in the by-subject or by-pathogen microbiological response and will be provided in separate listings ([Section 13.3.1](#); [Table 13.3.1-2](#)).

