13.2.4 Hospitalization Prior to the Follow-Up Visit

An assessment of hospitalization (defined as readmission to the hospital if previously hospitalized on or after study drug initiation [Day 1], or initial hospital admission (if not previously hospitalized) for any reason between the initiation of study drug (Day 1) and FU will be made programmatically based on information collected in the eCRF.

For the purposes of this secondary efficacy assessment, “hospital admission” is defined as inpatient admission for at least 24 h in an acute care facility (including inpatient hospital ward or emergency room); in contrast, admission to nursing homes, assisted living facilities, rehabilitation units, or acute care facilities (hospital wards or emergency rooms) for less than 24 h is not considered a formal hospital admission. The assessment of hospitalization within 30 days of study drug initiation is defined in [Table 13.2.4-1](#).

Of note, adverse events that lead to readmission or new admission to the hospital will meet SAE criteria, as defined in [Section 14.1.4](#).

Table 13.2.4-1 Hospitalization Prior to the Follow-Up Visit

Outcome	Definition
Hospitalization Prior to FU	Meets any of the following criteria: 
 • Hospital readmission for any reason between Day 1 and FU Visit, if previously hospitalized and discharged • Initial hospital admission for any reason between Day 2 and FU Visit, if not previously hospitalized on Day 1

Table 13.2.4-1 Hospitalization Prior to the Follow-Up Visit

Outcome	Definition
No Hospitalization Prior to FU	Does not meet the criteria for hospitalization within 30 days of study drug initiation as defined above, or till FU whichever is earlier.
Indeterminate	Study data are missing for evaluation of efficacy at FU Visit for any reason, including lost to follow-up.

Abbreviations: FU = Follow-Up

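### The hospitalization endpoint counts an index stay that never ends as clinical success and does not say how death before follow-up is scored

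*Combined protocol and SAP*

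**What the plan says.** Table 13.2.4-1 of the protocol gives two ways to be an event. For subjects already hospitalized: "Hospital readmission for any reason between Day 1 and FU Visit, if previously hospitalized and discharged". For the others: "Initial hospital admission for any reason between Day 2 and FU Visit, if not previously hospitalized on Day 1". The No Hospitalization row is a residual: "Does not meet the criteria for hospitalization within 30 days of study drug initiation as defined above, or till FU whichever is earlier". It does not require the subject to be alive or out of hospital. The Indeterminate row reads "Study data are missing for evaluation of efficacy at FU Visit for any reason, including lost to follow-up". Neither death nor a continuing index stay appears in the table.

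The prose above the table differs on timing: it starts the window for a first admission at study drug initiation on Day 1, where the table starts it on Day 2.

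Section 16.2.3.2 places "lack of readmission or new admission to the hospital" among the variables measuring clinical success, and adds: "The difference between treatment groups in clinical success and 2-sided 95% CI for the difference also will be included in the tabulation". Section 13.1 specifies the ITT population. Section 8.1 allows treatment as an inpatient or an outpatient, so index admissions on Day 1 are expected.

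**The concern.** Death and a stay that never ends both prevent the recorded event from happening: neither subject can be readmitted. If such subjects land in the favourable category, the success rate is too high. An arm with more of them can then look as good as, or better than, an arm with fewer.

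The protocol handles death differently elsewhere. In Table 13.2.1-1 "Death from any cause prior to Day 4" is non-response, and Table 13.2.2-1 makes death before the EOT or TOC assessment a clinical failure. Those endpoints stop at TOC (Day 12 to 18), while FU is Day 28 to 34 (Section 8.4). Hospitalization is the only efficacy variable listed in Section 13.1 that reaches FU, so a death after TOC is unfavourable in no efficacy endpoint. Section 13.2.4 derives the outcome programmatically, so an unstated rule would be settled in the programming.

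**Working it through.** **The plan's own figure.** The protocol gives no expected rate for hospitalization. Its only precision statement (Section 16.2.1) is for Day 4 response: 78% of 75 subjects, CI 66.9% to 86.7%. Clopper-Pearson limits at x = 0.78 × 75 = 58.5 are 66.94% to 86.75%, which agrees to rounding. This confirms 75 as the planned arm size used below.

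**Applying Table 13.2.4-1 case by case.**

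1. *Inpatient at first dose, still in that stay at FU.* The first criterion fails (never discharged). The second fails (hospitalized on Day 1). FU data exist, so Indeterminate does not apply. Result: No Hospitalization, tabulated as success.
2. *Death before FU with no new admission.* Neither criterion is met, so the residual row fits. There is also no FU evaluation, so the Indeterminate row fits. No precedence is stated. Result: success or indeterminate, never failure.
3. *Death during the index stay.* The same ambiguity as case 2.
4. *Death after a qualifying admission or readmission.* Already an event, so not affected.

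**Size.** One subject = 1/75 = 1.33 points; three = 3/75 = 4.0 points. The documents give no expected counts. The table assumes 4 admissions or readmissions in an arm of 75 and keeps indeterminate subjects in the ITT denominator.

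| Deaths without admission | Unended index stays | Both scored success | Death indeterminate, stay success | Both unfavourable |
|---|---|---|---|---|
| 0 | 3 | 71/75 = 94.7% | 71/75 = 94.7% | 68/75 = 90.7% |
| 1 | 1 | 71/75 = 94.7% | 70/75 = 93.3% | 69/75 = 92.0% |
| 3 | 0 | 71/75 = 94.7% | 68/75 = 90.7% | 68/75 = 90.7% |

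Clopper-Pearson limits are 86.9% to 98.5% for 71/75, 85.1% to 97.8% for 70/75, 83.4% to 97.0% for 69/75 and 81.7% to 96.2% for 68/75. In the last row, scoring deaths as indeterminate leaves the success rate correct, but shows 4 failures where there were 4 + 3 = 7 unfavourable outcomes.

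**Direction of the comparison (assumed counts).** Arm X has 4 readmissions and no unended stays: 71/75 = 94.7%. Arm Y has 3 readmissions and 3 unended stays: 72/75 = 96.0% as written, 1/75 = 1.3 points better than X. With the stays counted as non-success, Y is 69/75 = 92.0%, 2/75 = 2.7 points worse.

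**The cited mortality.** Section 6.1 quotes 4.0% to 18.0% short-term mortality. Applied to 75 subjects this is 3 to 13.5 deaths, but it describes hospitalized patients generally. This trial also takes outpatients, stops at a PORT score of 105 and excludes subjects needing intensive care. Deaths after a qualifying admission are also already events. The range is an upper-side guide, not an estimate of misclassified subjects.

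**The case against.** A reader might infer that the table scores a death without admission as success. The text does not support that: a subject who has died has no FU data, the Indeterminate row covers data missing for any reason, and Section 16.2.3.2 keeps indeterminate as its own category. Section 16.4 also leaves dropouts and missing data to the SAP, and no such rules appear in the text available. The SAP may therefore settle the classification of deaths. It does not reach the unended stay, where nothing is missing.

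The Day 1 wording in the prose would make an admission beginning on Day 1 after dosing an event in itself, whether or not it ends. The unended-stay defect is therefore certain only for subjects already in hospital at first dose. This objection stands, and it exposes a conflict between prose and table that needs resolving anyway.

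The endpoint is named for hospitalization and the secondary objective is worded that way, so a composite with death measures something broader. That is true, and is why the admission-only count should stay.

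Finally, this is one secondary variable in an exploratory study with no formal comparisons (Section 16.2), deaths are reported as SAEs (Sections 14.1.4 and 14.1.5), and nothing in the documents suggests many subjects will still be in an index stay around Day 31. All of that limits the consequence. It does not make the classification right.

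**Conclusion.** The point holds in two parts. The first is definite: a subject in hospital at first dose and never discharged by FU is tabulated as a clinical success for not being hospitalized. The second is a gap: death before FU without a qualifying admission has two possible categories, no rule to choose between them, and no unfavourable option, unlike the Day 4, EOT and TOC endpoints.

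The success rate and its difference CI can therefore favour an arm with more unended stays and, under the No Hospitalization reading, more deaths. Under the Indeterminate reading, deaths do not raise the success count but failures are undercounted. The size is 1.33 points per misclassified subject; 1.3 to 4.0 points rests on an assumed 1 to 3 such subjects in an arm of 75. The documents do not support a firmer figure or the use of the cited mortality range as a forecast. The definition should be corrected, but the primary analysis is not affected.

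**What to change.** In Table 13.2.4-1 and the SAP:

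- Define the unfavourable outcome as hospital admission, readmission or death from any cause before FU, and state that death takes precedence over Indeterminate.
- Tabulate subjects still in the index admission at FU as a separate row that is not counted as success.
- Reconcile the Day 1 window in the prose of Section 13.2.4 with the Day 2 window in the table.
- Keep the admission-only count as a supportive line, so that the stated hospitalization objective is still reported.

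Section 16.2 has the SAP finalized before database lock, so the rule can be fixed in advance. No new data collection appears necessary: readmission is already derived from the eCRF, and deaths are recorded as SAEs. The cost is a wording change, a slightly less favourable reported rate, and a composite that is broader than the stated objective.
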